6.7 Dose Modifications for Pancreatic Toxicity

XL184 should be held if patient experiences Grade 3 asymptomatic amylase or lipase elevation. Elevated laboratory parameters should be checked at least twice weekly until \leq Grade 1.

If lab values do not resolve to \leq 1 Grade within 7 days of interruption or if toxicity recurs with re-challenge, then this will be considered dose-limiting per [section 5.5.1](#). XL184 will then be dose-reduced according to [Section 6.2.1](#) when eligibility criteria is met.

6.8 Dose Modifications for Diarrhea

See [Appendix XIV](#) for specific guidelines for supportive care measures for patients who develop therapy-associated diarrhea.

- If dose-limiting Grade 3 (> 3 days) or Grade 4 therapy-associated diarrhea is experienced by a patient despite maximal use of anti-diarrheal medications, the dose of XL184 should be reduced per [Appendix IIB](#).

7.0 SUPPORTIVE CARE AND OTHER CONCOMITANT THERAPY**7.1 Concurrent Anticancer Therapy**

Concurrent cancer therapy, including chemotherapy, radiation therapy, immunotherapy, or biologic therapy may NOT be administered to patients receiving study drug. If these treatments are administered the patient will be removed from protocol therapy.

7.2 Investigational Agents

No other investigational agents may be given while the patient is on study.

7.3 Supportive Care

Appropriate antibiotics, blood products, antiemetics, fluids, electrolytes and general supportive care are to be used as necessary. See [Section 7.5](#) for drugs that should not be used concomitantly due to potential interactions with XL184.

Diarrhea is a common side effect of XL184. Loperamide should be used at the first sign of significant diarrhea (See [Appendix XIV](#)).

Palmar-plantar erythrodysesthesia syndrome (PPE; also known as hand-foot syndrome) is a common side effect of XL184. Careful attention should be paid to skin exams and supportive care instituted early if any swelling or erythematous skin changes or symptoms of pain or burning/tingling are noted. Patients should be instructed to apply moisturizing creams, avoid any trauma, harsh chemicals and limit hot water exposure. Topical steroid creams may be used and consider early dermatology referral.

7.4 Growth Factors

Growth factors that support platelet or white cell number or function can only be administered for culture proven bacteremia or invasive fungal infection. The Study Chair should be notified before growth factors are initiated.

7.5 Concomitant Medications

Proton pump inhibitors (PPIs) and H₂-antagonists should be avoided if possible (See [Section 9.1.6](#)).

Medications that are strong inhibitors or inducers of CYP3A4 should be avoided (see

[Appendix IX](#)). Corticosteroids may induce CYP3A4 and are therefore not routinely recommended on study unless deemed absolutely necessary or when used in stable or decreasing doses from the time of study enrollment.

The use of enzyme inducing anticonvulsants is not permitted. See [Appendix XIII](#) for a list of unacceptable enzyme inducing and recommended non-enzyme inducing anticonvulsants.

XL184 has been associated with prolonged QTc, so medications that prolong QTc are prohibited and medications that may prolong QTc should be avoided when possible (see [Appendix XV](#)).

7.6 **Surgery**

Patients should not have elective surgical procedures while on therapy. For patients who require emergent or urgent procedures, therapy may not be restarted until 28 days after major procedures and 7 days after minor procedures such as line replacement (3 days for external lines [e.g. Hickman or Broviac]), as detailed in [section 4.2.6](#).

7.7 **Concurrent Anti-Hypertensive Therapy**

The algorithm in [Section 6.4](#) will be used to grade and manage XL184 related hypertension. Should initiation of anti-hypertensive therapy be required, single agent therapy (commonly including the calcium channel blockers amlodipine or nifedipine, which are permissible without discussion with the study chair) should be started and the blood pressure should be monitored at least twice weekly until BP is within the 95th percentile for age, height, and gender per [Section 6.4](#).

7.8 **Management of Hypothyroidism**

Patients with Grade 2 hypothyroidism adequately managed with thyroid hormone replacement may continue on protocol therapy. Patients with Grade 3 or greater hypothyroidism will be considered to have had a dose-limiting toxicity. These patients should be managed according to [Section 6.2](#) and should also be evaluated by an endocrinologist for further management. Patients who enter the study on thyroid replacement should have their medication adjusted to maintain TSH in the normal range.

8.0 EVALUATIONS/MATERIAL AND DATA TO BE ACCESSIONED

8.1 Required Clinical, Laboratory and Disease Evaluation

All clinical and laboratory studies to determine eligibility must be performed within 7 days prior to enrollment unless otherwise indicated. Laboratory values used to assess eligibility (see [Section 4.0](#)) must be no older than seven (7) days at the start of therapy. Laboratory tests need **not** be repeated if therapy starts **within** seven (7) days of obtaining labs to assess eligibility. If a post-enrollment lab value is outside the limits of eligibility, or laboratory values are older than 7 days, then the following laboratory evaluations must be re-checked within 48 hours prior to initiating therapy: CBC with differential, bilirubin, ALT (SGPT) and serum creatinine. If the recheck is outside the limits of eligibility, the patient may not receive protocol therapy and will be considered off protocol therapy. Imaging studies must be obtained within 14 days prior to start of protocol therapy (repeat the tumor imaging if necessary).

STUDIES TO BE OBTAINED	Pre-Study	During Cycle 1	During Cycles 2 & 3	Prior to Subsequent Cycles [^]	30 days, 6 months, and annually up to 60 months ^^
History	X	Weekly		X ¹⁵	X
Physical Exam with vital signs	X	Weekly		X ¹⁵	X
Blood pressure ¹	X	Weekly	Every other week (Cycle 2)	X ¹⁵	
Height, weight, BSA	X			X ¹⁵	X
Performance Status	X				
Pregnancy Test ²	X			X ¹⁵	
CBC, differential, platelets	X	Weekly ^{3,4}	Every other week	X ^{3,4,15}	
Urinalysis ⁵	X	Weekly		X ¹⁵	
Electrolytes including Ca ⁺⁺ , PO ₄ , Mg ⁺⁺	X	Weekly	Every other week	X ¹⁵	
Creatinine, ALT, bilirubin	X	Weekly	Every other week	X ¹⁵	
Albumin	X			X ¹⁵	
Amylase, lipase	X	Weekly	Every other week	X ¹⁵	
PT and INR	X				
TSH ⁶	X	Once mid-cycle (days 15-22)		X ¹⁵	
RET mutation status (germline and tumor) for patients with MTC (if available)	X				
CEA and calcitonin for patients with MTC ⁷	X	End of Cycle 1		Every other cycle x 2 then q 3 cycles	

STUDIES TO BE OBTAINED	Pre-Study	During Cycle 1	During Cycles 2 & 3	Prior to Subsequent Cycles [^]	30 days, 6 months, and annually up to 60 months ^{^^}
Tumor Disease Evaluation ^{8, 14}	X	End of Cycle 1		Every other cycle x 2 then q 3 cycles ^{8, 14}	
EKG (including QTc interval) ¹³	X	End of Cycle 1	End of Cycle 2	Every other cycle x 2 then q 3 cycles ¹³	
Plain radiograph tibial growth plate ⁹	X			X ⁹	
Patient Diary ¹⁰		Weekly		X	
Pharmacokinetics¹¹	COMPLETE	X	X	X	
Pharmacodynamics ¹²	X	X			
Tissue Studies ¹²	X				

[^] Studies may be obtained within 72 hours prior to the start of the subsequent cycle.

^{^^} Required observations beginning 30 days, 6 months (\pm 14 days), and annually (\pm 30 days) following the last dose of investigational agent until patient is off study (see [Section 10.2](#)).

¹ Blood pressure will be measured with an appropriate sized cuff at rest. Please note that 3 serial blood pressures should be obtained and averaged to determine baseline BP (See [Section 6.4](#)). Blood pressure measurement will be repeated within the same day if the blood pressure (BP) is elevated ($>$ 95th percentile for age, height, and gender). If both BP measurements are $>$ 95th percentile for age, height, and gender, follow the guidelines in [Section 6.4](#). Patients with confirmed elevated BP at any time should have BP measurements performed at least twice weekly until BP is within the 95th percentile for age, height, and gender (See [Appendix VIII](#)).

² Males or females of reproductive potential may not participate unless they have agreed to use both a medically accepted barrier method of contraceptive method (e.g., male or female condom) and a second effective method of birth control during protocol therapy and for at least 4 months after the last dose of XL184. Abstinence is an acceptable method of birth control.

³ If patients have Grade 4 neutropenia then CBCs should be checked at least every other day (see [Section 6.1](#)).

⁴ If patients develop Grade 4 thrombocytopenia then CBCs should be checked every 3 to 4 days (see [Section 6.1](#)).

⁵ See [Appendix VII](#) for UPC rationale and calculation and [Section 6.3](#) for dose modifications if UPC $>$ 1.9. If patient is being followed for prior proteinuria and UPC is obtained, urinalysis is not required. If 24 hour urine for protein is obtained, both urinalysis and UPC are not required. If patient has Grade 3 proteinuria (urine protein/creatinine (P/C) ratio $>$ 1.9), a second measurement should be obtained within 72 hours.

⁶ Patients found to have an abnormal TSH level should have a free T4 level measured.

⁷ Calcitonin measurements should be obtained in the fasting state.

⁸ Tumor Disease Evaluation should be obtained on the next consecutive cycle after initial documentation of either a PR or CR. Please note that for solid tumor patients, if the institutional investigator determines that the patient has progressed based on clinical or laboratory evidence, he/she may opt not to confirm this finding radiographically.

⁹ Plain radiographs of at least one tibial growth plate should be obtained in all patients prior to first dose of protocol therapy. In patients with open growth plates, follow-up plain radiographs of the same growth plate(s) should be obtained according to [Section 8.2.1](#).

- 10 Patient diary (see [Appendix III](#)) should be reviewed and uploaded into RAVE weekly during Cycle 1, and then after completion of each treatment cycle.
- 11 See [Section 8.4](#) and [Appendix V](#) for timing of PK studies. **COMPLETE**
- 12 See [Section 8.5](#) for timing of Pharmacodynamic/Biomarker studies and details regarding tumor tissue submission. Archival tumor tissue should be submitted for all patients. If a patient does not have tissue available, the study chair must be notified prior to enrollment.
- 13 Patients with prolonged QTc should have correctable causes of prolonged QTc addressed if possible, including medications (See [Appx. XV](#)) and correction of electrolyte abnormalities (incl. Ca^{++} and Mg^{++}). If there is no evidence of QTc prolongation after completion of 6 cycles of therapy, further EKGs are not required.
- 14 Patients currently enrolled on Part B of the study should be evaluated every 6 months.
- 15 Patients currently enrolled on Part B of the study should be evaluated/have this test performed every other cycle.

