- Creatinine clearance or radioisotope GFR $\geq 70\text{ml/min}/1.73\text{ m}^2$ or
- A serum creatinine based on age/gender as follows:

Age	Maximum Serum Creatinine (mg/dL)	
	Male	Female
2 to < 6 years	0.8	0.8
6 to < 10 years	1	1
10 to < 13 years	1.2	1.2
13 to < 16 years	1.5	1.4
≥ 16 years	1.7	1.4

The threshold creatinine values in this Table were derived from the Schwartz formula for estimating GFR (Schwartz et al. J. Peds, 106:522, 1985) utilizing child length and stature data published by the CDC.

- Urine protein: $\leq 30\text{ mg/dl}$ in urinalysis or $\leq 1+$ on dipstick, unless quantitative protein is $< 1000\text{ mg}$ in a 24 h urine sample.

4.1.8.3 Adequate Liver Function Defined as:

- Bilirubin (sum of conjugated + unconjugated) $\leq 1.5 \times$ upper limit of normal (ULN) for age
- SGPT (ALT) $\leq 110\text{ U/L}$. For the purpose of this study, the ULN for SGPT is 45 U/L.
- Serum albumin $\geq 2.8\text{ g/dL}$.

4.1.8.4 Adequate coagulation status Defined As:

- PT and INR $\leq 1.5 \times$ ULN

4.1.8.5 Adequate Pancreatic Function Defined As:

- Serum amylase $\leq 1.5 \times$ ULN and
- Serum lipase $\leq 1.5 \times$ ULN

THIS PROTOCOL IS FOR RESEARCH PURPOSES ONLY, SEE PAGE 1 FOR USAGE POLICY

4.1.8.6 Adequate Blood Pressure Control defined as:

A blood pressure (BP) \leq the 95th percentile for age, height, and gender ([Appendix VIII](#)) measured as described in [Section 6.4](#), and not receiving medication for treatment of hypertension. Please note that 3 serial blood pressures should be obtained and averaged to determine baseline BP (See [Section 6.4](#)).

4.1.8.7 Central Nervous System Function Defined as:

Patients with seizure disorder may be enrolled if receiving non-enzyme inducing anticonvulsants and well controlled. See [Appendix XIII](#) for a list of recommended non-enzyme inducing anticonvulsants.

4.1.8.8 Adequate Cardiac Function Defined As:

- No history of congenital prolonged QTc syndrome, NYHA Class III or IV congestive heart failure (CHF)
- No clinically significant cardiac arrhythmias, stroke or myocardial infarction within 6 months prior to enrollment
- QTc \leq 480 msec. Note: Patients with Grade 1 prolonged QTc (450-480 msec) at the time of study enrollment should have correctable causes of prolonged QTc addressed if possible (i.e. electrolytes, medications). See [Appendix XV](#) for a list of drugs that prolong QTc.

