5.2 Criteria for Starting Subsequent Cycles

A cycle may be repeated every 28 days if the patient has at least stable disease, has again met laboratory parameters as defined in the eligibility sections [4.1.8.1- 4.1.8.3](#) and [4.1.8.5](#), and has not experienced study-drug related adverse events warranting permanent discontinuation.

Patients who have a delay in starting subsequent cycles for resolution of toxicity should also have the required observations in [Section 8.1](#) until the start of the next cycle.

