5.5.1 Non-Hematological Dose-Limiting Toxicity

5.5.1.1 Any Grade 3 or Grade 4 non-hematological toxicity attributable to the investigational drug with the specific exclusion of:

- Grade 3 nausea and vomiting of < 3 days duration
- Grade 3 diarrhea \leq 3 days duration
- Grade 3 liver enzyme elevation, including ALT/AST/GGT/bilirubin, that return to levels that meet initial eligibility criteria or baseline within 7 days of study drug interruption and that does not recur upon re-challenge with XL184. Note: For the purposes of this study the ULN for ALT is defined as 45 U/L. See [section 6.6](#) for dose modifications for liver toxicity.
- Grade 3 or 4 fever < 5 days duration.
- Grade 3 infection < 5 days duration.
- Grade 3 hypophosphatemia, hypokalemia, hypocalcemia or hypomagnesemia responsive to supplementation
- Grade 3 asymptomatic amylase or lipase elevation that resolves to \leq Grade 1 within 7 days of study drug interruption and that does not recur upon re-challenge with XL184. See [section 6.7](#) for dose modifications for pancreatic toxicity.
- Grade 3 proteinuria (urine protein/creatinine (P/C) ratio $>$ 1.9) unless it is confirmed with a second measurement within 72 hours.

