6.3 Dose Modifications for Proteinuria

THIS PROTOCOL IS FOR RESEARCH PURPOSES ONLY, SEE PAGE 1 FOR USAGE POLICY

- If urinalysis shows \geq trace protein then obtain UPC.
- If the urine protein/creatinine (P/C) ratio ≤ 1.9 continue XL184. If patient has Grade 3 proteinuria (urine protein/creatinine (P/C) ratio > 1.9), a second measurement should be obtained within 72 hours. A second confirmation of Grade 3 proteinuria will be considered a DLT.
- If the second measurement confirms Grade 3 proteinuria (urine protein/creatinine (P/C) ratio > 1.9), then interrupt XL184 treatment and reassess weekly.
- If XL184 is held for ≥ 14 days then remove from protocol therapy. If the urine protein/creatinine (P/C) ratio decreases to ≤ 1.9 in < 14 days then resume XL184 at a lower dose as outlined in [Section 6.2.1](#).
- Monitor the UPC weekly for 2 consecutive weeks once protocol therapy resumes.

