APPENDIX VII: URINE PROTEIN TO CREATININE (UPC) RATIO**Clinical Meaning of UPC**

There is a good correlation between the ratio of urine protein to creatinine concentrations (UPC) in a random urine sample and the amount of protein excreted in a 24-hour urine collection period.¹⁸ Thus, the UPC allows for an estimation of the 24-hour urine protein excretion from a random sample. The creatinine excretion is fairly constant throughout the day regardless of changes in urine flow rate:

- Men excrete 20 mg to 25 mg of creatinine/kg of body weight/day
- Women excrete 15 mg to 20 mg of creatinine/kg of body weight/day
- Normal protein excretion is <100 mg to 150 mg per 24 hours.
- The UPC ratio is roughly equal to the 24 hour urine protein excretion in g/day

Calculating UPC Ratio

UPC ratio = (Urine protein [mg/dL]) / (urine creatinine [mg/dL]) = numerically equivalent to grams (g) protein excreted in urine over 24 hours.

Example: If a subject has a urine protein of 90 mg/dL and urine creatinine of 30 mg/dL,

$$\text{then UPC ratio} = \frac{90 \text{ (mg/dL)}}{30 \text{ (mg/dL)}} = 3$$

Result UPC is 3 correlating to roughly 3g of protein excretion in a 24-hour period.

Units for UPC ratio

UPC is a calculated ratio. The guidelines in the protocol are based on having urine protein and urine creatinine measured in the same units (e.g., mg/dL). The SI units for urine protein and urine creatinine are not the same, so these must be converted to mg/dL before calculating the ratio. For reference, the conversion factors for commonly used units for protein and creatinine are provided below.

Starting units	Conversion to mg/dL
Protein (g/L)	Multiply by 100
Creatinine (μmol/L)	Divide by 88.4
Creatinine (mmol/L)	Multiply by 11.3

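### A 24-hour urine protein may replace UPC on treatment, but the proteinuria hold and DLT limit is written only as a UPC, and in a small child the two limits can disagree

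*Combined protocol and SAP*

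**What the plan says.** Footnote 5 sits on the urinalysis row of the Section 8.1 schedule, so it covers on-treatment visits as well as baseline. It states: "If 24 hour urine for protein is obtained, both urinalysis and UPC are not required".

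The action rules use a different measure. Section 5.5.1.1 gives Grade 3 proteinuria as a UPC above 1.9 and excludes it as a DLT "unless it is confirmed with a second measurement within 72 hours". Section 6.3 asks for a UPC when urinalysis shows trace protein or more, a repeat within 72 hours if the ratio is above 1.9, and interruption if that is confirmed: "A second confirmation of Grade 3 proteinuria will be considered a DLT". The return to treatment is also defined by the ratio.

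The one 24-hour limit is in the entry criteria. Section 4.1.8.2 accepts up to 1+ "on dipstick, unless quantitative protein is" below 1000 mg in 24 hours. Section 5.2 carries this onto treatment: a new cycle may start if the patient "has again met laboratory parameters as defined in the eligibility sections" 4.1.8.1 to 4.1.8.3 and 4.1.8.5.

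Appendix VII links the two measures: "The UPC ratio is roughly equal to the 24 hour urine protein excretion in g/day". Its creatinine excretion rates are for men (20 to 25 mg/kg/day) and women: "Women excrete 15 mg to 20 mg of creatinine/kg of body weight/day".

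**The concern.** A permitted substitute test should lead to the same action as the test it replaces. Here the substitute has a pass limit at cycle start but no stated hold or DLT limit, and the pass limit is a fixed number of milligrams while the hold limit scales with creatinine output, and so with body size. The trial admits children from 2 years of age and from 0.35 m² at the dose level in use, and the loperamide table in Appendix XIV has a band below 13 kg.

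At stake is a small child who starts the next cycle on a passing 24-hour result, without the 72-hour repeat and possible hold that Section 6.3 would have required had UPC been measured. Proteinuria is a known effect of the drug: Section 2.6 records one Cycle 1 DLT of Grade 3 proteinuria with Grade 2 hypertension, at 55 mg/m².

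**Working it through.** **Inputs.** UPC limit 1.9 (Sections 5.5.1.1 and 6.3). 24-hour limit below 1000 mg (Section 4.1.8.2). Creatinine rate r = 15, 20 or 25 mg/kg/day (Appendix VII, adults). The documents give no pediatric rate, so applying these to children is an assumption; r = 30 is added as a stress test.

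**The plan's own figure.** Appendix VII's example is 90 / 30 = 3, read as about 3 g/day. This reproduces. The reading as grams per day needs about 1000 mg of creatinine a day, which means 1000/25 = 40.0 kg to 1000/15 = 66.7 kg at the appendix's own rates.

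**Formulas**, with W the weight in kg:
- UPC = 24-hour protein (mg) / (r × W).
- The 1.9 limit as protein per kg per day = 1.9 × r.
- Weight at which 1000 mg equals UPC 1.9 = 1000 / (1.9 × r).

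| r (mg/kg/day) | 1.9 limit (mg/kg/day) | Crossover weight (kg) | UPC at 999 mg: 15 kg | 20 kg | 25 kg | 30 kg | 40 kg |
|---|---|---|---|---|---|---|---|
| 15 | 28.5 | 35.1 | 4.44 | 3.33 | 2.66 | 2.22 | 1.67 |
| 20 | 38.0 | 26.3 | 3.33 | 2.50 | 2.00 | 1.67 | 1.25 |
| 25 | 47.5 | 21.1 | 2.66 | 2.00 | 1.60 | 1.33 | 1.00 |
| 30 (stress test) | 57.0 | 17.5 | 2.22 | 1.67 | 1.33 | 1.11 | 0.83 |

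Below the crossover weight, some passing results exceed the hold limit. At 20 kg the 24-hour protein equal to UPC 1.9 is 1.9 × 15 × 20 = 570 mg at the lowest rate and 1.9 × 25 × 20 = 950 mg at the highest, so the range that passes while exceeding 1.9 runs from wide to narrow. At 40 kg there is no gap at any rate shown. A rate below 15 would widen it: at an assumed 10 mg/kg/day the crossover is 1000 / 19 = 52.6 kg.

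**Two routes to a 24-hour result.**
1. A dipstick is done first and shows trace or more. Section 6.3 directs a UPC; footnote 5 says none is required once a 24-hour protein is obtained. The texts conflict, and neither says which governs.
2. The 24-hour collection replaces urinalysis outright. The Section 6.3 trigger never occurs, and no stated proteinuria hold rule applies to the result.

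**Time to the next routine check after one replaced test.** About 7 days in Cycle 1, where urinalysis is weekly. After that the schedule shows urinalysis before each cycle, so 28 days. In Part B, "Patients currently enrolled on Part B of the study should be evaluated/have this test performed every other cycle", so 2 × 28 = 56 days.

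**The case against.** The strongest reply is that Section 6.3 is the dose-modification rule and footnote 5 only a scheduling note, which itself points to Section 6.3. On that reading a child with a positive dipstick gets a UPC whatever the footnote waives. This stands: a reader might infer that the protocol steers such a child past UPC, and the documents do not support that. For this route the defect is contradictory wording. The clean gap needs a site to collect a 24-hour urine with no urinalysis, and nothing in the protocol specifically prompts that.

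Other safeguards also remain. Section 5.2 re-applies the serum albumin minimum of 2.8 g/dL at cycle start. Any attributable Grade 3 or 4 non-hematological toxicity is a DLT, apart from the listed exclusions, under CTCAE v4.0. How that scale grades a 24-hour result in a child is not in the documents, so it would be too strong to say that such a result can never be graded or lead to a hold.

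Appendix VII does offer a conversion, but it does not close the gap. Read literally, 999 mg becomes a UPC of about 1.0 and looks safe, which understates the ratio in a child whose creatinine output is well below 1 g/day.

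Reach is limited too. The adverse event list in Section 9.1.7 places proteinuria under rare but serious (<3%). Patients must swallow intact tablets (Section 4.2.3), which may thin out the smallest children. The PK work is marked complete, so enrollment may be over, and the documents do not say whether any patient still on treatment weighs under 35 kg.

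**Conclusion.** The point holds as a minor gap in an on-treatment safety rule. Footnote 5 lets a test with no stated proteinuria hold or DLT limit replace the only test that has one. Where the 24-hour pass limit does apply, at cycle start, it can pass a small child whose UPC would exceed 1.9. The weight range, below about 21 to 35 kg, rests on adult creatinine rates; at 30 mg/kg/day it shrinks to below 17.5 kg. The mismatch itself comes from comparing a fixed mass with a ratio that depends on body size.

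A reader might go further and infer that proteinuria DLTs were missed or that the recommended dose is in doubt. The documents do not support either. The recorded proteinuria DLT was detected, Cycle 1 checks are weekly, and Section 2.6 bases the choice of 40 mg/m² on toxicity at 55 mg/m² and in later cycles, with comparable exposure across doses. Few patients can be affected; the plan called for 6 under 12 years at 40 mg/m², and no weights are given.

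**What to change.** Make two text edits.

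1. Footnote 5: a 24-hour collection does not waive UPC unless creatinine is measured in the same collection and the protein/creatinine ratio is reported from it.
2. Section 6.3: state that the existing 1.9 confirm, hold and DLT limit applies to that ratio, including at cycle start, and that the 72-hour confirmation may be a spot UPC.

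A simpler alternative is to remove UPC from the footnote's waiver, preferably adding that a UPC is still obtained, because Section 6.3 otherwise triggers it from a urinalysis. An optional note in Appendix VII could say that UPC matches grams per day only at about 1 g/day of creatinine. The 1.9 threshold and the entry limit can stay as they are.

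The cost is one creatinine assay on urine already collected, with no extra visit; a further sample is needed only if the ratio exceeds 1.9, when Section 6.3 already asks for a repeat. The downside is an occasional hold or delay in a small child. The simpler alternative costs a spot UPC instead.
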